3. GENERAL CHARACTERISTICS ANALYSES

3.1 SUBJECT DISPOSITION

The following patient data will be tabulated:

- The number of patients in each analysis set
- The number and percentage of patients by country and investigator
- The number and percentage of patients for each period/analysis visit.
- The number and percentage of patients for each period/analysis visit who had a missed visit and who had a phone call visit due to COVID-19 (as documented in the CRF comment).
- Descriptive statistics and tabulation in weeks of the cycle duration (see section 2.2.1), calculated as cycle end date – cycle start date + 1 day
- Descriptive statistics of the study duration, calculated as study end date – study start date + 1 day.
- Frequency tabulation of the study duration per 6-monthly period, showing the number and percentage in each category and additionally cumulative number and percentages. Categories are defined as follows: <6 months (< 168 days); 6 to <12 months (168 - 350 days); 12 to <18 months (351 - 532 days); 18 to <24 months (533 - 715 days); 24 to <30 months (716 - 897 days); 30 to <36 months (898 - 1080 days); 36 to <42 months (1081 - 1262 days).
- The number and percentage of patients who completed or discontinued the study as documented on the study termination page and the number and percentage of patients for each study discontinuation reason.
- The number and percentage of patients who completed or discontinued the study as documented on the study termination page and the number and percentage of patients for each study discontinuation reason by cycle.
- The number and percentage of patients who completed or discontinued the treatment as documented on the end of treatment page and the number and percentage of patients for each treatment discontinuation reason.
- The number and percentage of patients who completed or discontinued the treatment as documented on the end of treatment page and the number and percentage of patients for each treatment discontinuation reason by cycle.

All information collected in the CRF concerning study and treatment discontinuation will be listed.

3.2 PROTOCOL DEVIATIONS

The number and percentage of patients with major protocol deviations will be tabulated, overall and per class of deviation.

All available information concerning major protocol deviations will be listed.

	Statistical Analysis Plan	
ARGX-113-1705	Final Analysis	Final 1.0 of 20SEP2022

3.3 DEMOGRAPHIC AND OTHER BASELINE CHARACTERISTICS

3.3.1 *Available data*

The following parameters will be collected during the roll-over visit:

- Demographics: sex at birth, women of childbearing potential, age, race, ethnicity, height, weight at screening, body mass index at screening, date of birth, date of signing informed consent form (IC).
- Baseline disease characteristics: date of diagnosis, MGFA Classification at 1704 screening and at diagnosis, receiving NSID as SoC (yes/no) at 1704 screening, AChR-Ab status (1704), MuSK-Ab status (1704), MG-ADL questionnaire (Total MG-ADL Score) at baseline (see 2.2.2), QMG (Total QMG Score) at baseline (see 2.2.2).

3.3.2 *Derivation rules*

The following parameters will be derived:

- Age category: 18-64 years, ≥ 65 years
- Japanese vs non-Japanese (including Hispanic or Latino, Not Hispanic or Latino and Not allowed to ask per local regulations)
- Region: Japan; US; rest of the world
- Time since diagnosis (years): $(\text{date of ICF} - \text{date of diagnosis})/365.25$.
Partially missing date of diagnoses will be imputed as follows:
 - Missing start day will be imputed with 1
 - Missing start day and month will be imputed with 1JAN

Note: Result will be rounded as detailed in section [2.3.3](#).

3.3.3 *Presentation of results*

Demographics will be presented using descriptive statistics for age, height, weight and BMI and frequency tabulations for age category, sex at birth, race, region, ethnicity, Japanese/non-Japanese patients.

Baseline disease characteristics will be presented using descriptive statistics for time since diagnosis, total MG-ADL score and total QMG score and frequency tabulations for MGFA Classification (at 1704 screening and at diagnosis), AChR-Ab and MuSK status in 1704 and Standard of Care (SoC).

All demographic data and baseline disease characteristics will be listed.

3.4 MEDICAL HISTORY AND CONCOMITANT DISEASES

3.4.1 *Available data*

Medical history findings are coded using the medical dictionary for regulatory activities (MedDRA), version 24.1 (SEP2021) into system organ classes and preferred terms. For each finding, a start and stop date or ongoing flag is collected.

3.4.2 *Derivation rules*

Medical history finding: not ongoing at roll-over visit, ended before date of signing informed consent.

	
Statistical Analysis Plan
	

ARGX-113-1705
	
Final Analysis
	
Final 1.0 of 20SEP2022

3.4.3 Presentation of results

Medical history (not ongoing at roll-over visit) and concomitant diseases (still ongoing at roll-over visit) will be tabulated in a separate table. Both tables will show:

- The number and percentage of patients with findings
- The number and percentage of patients with findings by system organ class and preferred term

All medical history data will be listed.

3.5 PRIOR AND CONCOMITANT THERAPIES

3.5.1 Available data

All therapies are coded using the March 2020 version of the WHO-DRUG. ATC selection is performed. ATC coding up to level 4 is available in the clinical database. For each therapy, a start date or prior flag and stop date or ongoing flag are collected.

3.5.2 Derivation rules

Based on their start and stop date, therapies will be allocated to each analysis period during which they were administered. A therapy can therefore be reported in more than one analysis period.

Analysis periods are defined in section 2.2.1. Therapies with (partially) missing dates will be allocated to each period unless the available parts of the therapy start or stop date or prior and ongoing flags provide evidence the therapy was not taken during that period.

Concomitant therapies are defined as therapies taken on or after the first OLE dose date.

3.5.3 Presentation of results

Concomitant therapies will be tabulated, by ATC class (level 1 and level 3) and generic term. This table will be provided overall, not by cycle.

All concomitant therapies data will be listed with detailed information about ATC classes.

3.6 STUDY DRUG ADMINISTRATION

3.6.1 Available data

For each study drug administration, the start and end date/times and the volumes will be recorded.

	
Statistical Analysis Plan
	

ARGX-113-1705
	
Final Analysis
	
Final 1.0 of 20SEP2022

3.6.2 Derivation rules

The following parameters will be derived:

- Number of administrations: number and percentage of patients who had 1, 2, 3 etc.... administrations per cycle and overall
- Actual dose (mg/kg) per administration per cycle, using categories <9mg/kg, 9-11 mg/kg, >11mg/kg.
- Treatment compliance per cycle defined as (number of doses received/4)*100%
- The actual dose in mg/kg will be calculated as =

$$\left(\frac{\text{actual volume extracted from vials (mL)} * 20 \text{ (mg/mL)}}{\text{actual volume extracted from vials (mL)} + \text{actual volume of NaCl solution added to IV bag (mL)}} \right) * \left(\frac{\text{actual volume infused (mL)}}{\text{last available patient weight (kg) before or at day of dosing}} \right)$$
- Note: As per protocol a variation of $\pm 10\%$ of the amount of 10 mg/kg, will not be considered an overdose/under dose.

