- ^e An unscheduled (UNS) visit can occur at the request of the patient or the investigator. During the UNS visit, additional assessments as indicated in the SoA can be performed at the discretion of the investigator, depending on the reason for the UNS visit.
- ^f No trial-related assessment is to be carried out before the patient has signed the informed consent form (ICF).
- ^g Assessments of disease severity should be completed predose on dosing days and before any other trial-specific assessment, except for obtaining informed consent at SEB and the weight assessment, if applicable. The MG-ADL scale should be administered before the QMG scale. Acetylcholinesterase inhibitors must be halted for at least 12 hours before the QMG assessment (consistent with the revised manual for the QMG test as recommended by the Myasthenia Gravis Foundation of America [MGFA]).
- ^h Suicidal ideation and behavior will be assessed predose on dosing days via a targeted question based on the Patient Health Questionnaire item 9 (PHQ-9).
- ⁱ The physical examination will be performed predose on dosing days. See Section 7.2.3 for an overview of the different assessments.
- ^j Weight will be measured at SEB, at the EoA/ED visit, and when there is an obvious weight change compared to the last weight assessment. Height will be measured at SEB.
- ^k Vital signs (supine blood pressure, heart rate, body temperature) will be performed predose on dosing days. It is recommended that the method used to measure body temperature at SEB is maintained throughout the trial for each patient.
- ^l ECG will be performed predose on dosing days.
- ^m Samples for clinical laboratory tests (hematology, clinical chemistry) will be collected predose on dosing days (see Appendix 3). Patients need to have fasted at least 8 hours prior to each sampling.
- ⁿ Urine samples will be collected predose on dosing days (see Appendix 3).
- ^o A urine pregnancy test will be performed predose on dosing days on the urine samples taken for urinalysis (only for women of childbearing potential, see DEFINITION OF TERMS).
- ^p Samples for pharmacodynamic (PD) biomarkers will be collected predose on dosing days (see Appendix 3). Anti-AChR antibodies will be measured in AChR-Ab seropositive patients only. Anti-MuSK antibodies will be measured in MuSK-Ab seropositive patients only. Information on the AChR/MuSK-Ab serotype (seronegative or seropositive) is available from trial ARGX-113-1704.

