6. TRIAL TREATMENT

6.1. Treatment Administered

Only patients who need (re-)treatment with efgartigimod, provided they are eligible (see Section 4.1 for the criteria for [re-]treatment), will be treated with efgartigimod.

Efgartigimod will be administered weekly for 3 weeks (4 infusions) as an IV infusion (total volume of 125 mL and a dose of 10 mg/kg of body weight) at visits 1, 2, 3 and 4 of each Treatment Period. A variation of $\pm 10\%$ of the amount, as planned per protocol, of efgartigimod administered to the patient will not be considered an overdose/underdose. In case of a significant ($>10\%$) change in body weight, the dose will be recalculated.

Although efgartigimod was administered over a period of 2 hours in all the other clinical trials conducted so far, in this trial, for patient's convenience and because no safety concerns are anticipated based on observations in the other trials, efgartigimod will be administered over a period of 1 hour. Please refer also to the IB, Section 6.3.

Details on infusion rate and time will be given in the IMP management manual (pharmacy manual).

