6.2. Identity of Investigational Medicinal Product

Efgartigimod will be supplied to the investigator or designated site staff at the investigational site, by and under the responsibility of the sponsor's designated IMP supply vendor, who will also provide the investigator with certificate of analysis, certificate of conformity and European Union Qualified Person (EU QP) release documents.

Efgartigimod will be provided as a sterile, colorless, clear concentrate for solution for IV administration in a formulation of [REDACTED]. The concentration of efgartigimod will be 20 mg/mL presented in a 20R vial. The extractable volume from 1 vial is 20 mL. Appropriate dilutions in a 0.9% saline solution will be made on site prior to administration.

Efgartigimod will be manufactured in accordance with Good Manufacturing Practice (GMP) regulations. Detailed instructions on efgartigimod management on site (including preparation) will be included in the IMP management manual (pharmacy manual).

The dose will be 10 mg/kg (total dose per efgartigimod infusion is capped at 1200 mg for patients with body weight ≥ 120 kg).

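### The SAP's fixed 9 and 11 mg/kg dose bands leave out the protocol's 1200 mg cap, so in heavy patients the exposure table does not show whether the planned amount was given

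*SAP*

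**What the plan says.** SAP 3.6.2 derives the actual dose in mg/kg for each administration in each cycle, "using categories <9mg/kg, 9-11 mg/kg, >11mg/kg". The dose is calculated from the volumes extracted, diluted and infused, and is divided by the "last available patient weight (kg) before or at day of dosing". A note under the formula cites the protocol for the rule that a variation of ±10% "of the amount of 10 mg/kg, will not be considered an overdose/under dose". SAP 3.6.3 plans a frequency table of these bands. SAP 3.6 mentions neither the dose cap nor the rule for recalculating the dose, and SAP 6.1 declares no change to the planned analysis.

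The protocol words the tolerance differently. In Protocol 6.1, a variation of ±10% "of the amount, as planned per protocol, of efgartigimod administered to the patient will not be considered an overdose/underdose". Protocol 6.2 then limits the planned amount: the "total dose per efgartigimod infusion is capped at 1200 mg for patients with body weight" of 120 kg or more. Protocol 6.1 adds that on a significant (>10%) "change in body weight, the dose will be recalculated".

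Weight is measured sparingly in Part A. Table 1, footnote j: "Weight will be measured at SEB, at the EoA/ED visit, and when there is an obvious weight change". In Part B it is measured at visit 1 of each treatment period and on obvious change (Protocol 5.2.2).

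**The concern.** The protocol measures over- and underdose against the planned amount in mg. The SAP measures them against 10 mg/kg at the latest weight, yet presents this as the protocol's rule. The two agree only while the planned amount equals 10 mg/kg of the weight in the denominator. They differ once the cap applies, and they can differ when weight changes without a new dose calculation.

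At stake is the reading of the exposure table in a trial whose primary objective is long-term safety. The three bands are the only planned tabulation of the amount given: compliance in SAP 3.6.2 counts doses received out of 4, and SAP 3.6.3 plans descriptive statistics only for the number of administrations and for compliance. If the bands use a different reference from the protocol, the table can put full planned infusions outside the central band and excess infusions inside it.

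**Working it through.** **Inputs.** Bands and denominator: SAP 3.6.2. Tolerance of ±10% of the planned amount, and recalculation on a >10% weight change: Protocol 6.1. Cap of 1200 mg from 120 kg, and vial strength of 20 mg/mL: Protocol 6.2. Total infusion volume of 125 mL: Protocol 6.1.

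**The SAP's own figures.** 10 × 0.90 = 9.0 and 10 × 1.10 = 11.0 mg/kg, so the bands are ±10% of 10 mg/kg. The cap starts where 10 mg/kg × 120 kg = 1200 mg.

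**The SAP formula.** When the whole bag is infused, it reduces to vial volume × 20 / last available weight. A capped patient of 140 kg has 60 mL drawn: (60 × 20 / 125) × (125 / 140) = 8.57 mg/kg.

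**Cap, full planned dose.** The result falls below 9 when 1200 / W < 9, that is W > 133.3 kg.

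| Weight (kg) | 1200 mg as mg/kg | SAP band | % of planned amount |
|---|---|---|---|
| 120 | 10.00 | 9-11 | 100 |
| 130 | 9.23 | 9-11 | 100 |
| 133.3 | 9.00 | 9-11 (limit) | 100 |
| 140 | 8.57 | <9 | 100 |
| 150 | 8.00 | <9 | 100 |

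This repeats at every full infusion while the weight used stays above 133.3 kg. If the protocol's own tolerance is used in full, the gap opens earlier. An infusion of 0.9 × 1200 = 1080 mg is within tolerance, but 1080 / 9 = 120, so it falls below 9 mg/kg at any weight above 120 kg (1080 / 125 = 8.64).

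**Cap, more than the planned amount.** The protocol's upper tolerance for a capped patient is 1.1 × 1200 = 1320 mg. The SAP's upper limit is 11 × W mg, which exceeds 1320 for every W above 120 kg. At 125 kg it admits 1375 mg. At 150 kg, 1500 mg is 1500 / 1200 = 125% of the planned amount, but 1500 / 150 = 10.0 mg/kg, in the central band.

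**Weight change without recalculation.** Assume that the dose was set on an earlier weight, was not recalculated, and that a new weight is on file. The tabulated dose is 10 / (1 + c), where c is the relative change.

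- c = −9.09%: 11.00 mg/kg, at the limit.
- c = −9.5%: 11.05. For example, 800 mg set at 80 kg and tabulated at 72.4 kg.
- c = −10%: 11.11.
- c = +10%: 9.09, still in 9-11. Falling below 9 would need a gain of more than 10/9 − 1 = 11.1%.

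So only a loss of more than 9.09% and up to 10% moves a full planned, uncapped dose out of the central band.

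**Against the planned amount.** With actual amount / planned amount, the 140 kg patient and the 80 kg patient above both read 100%, and the 1500 mg infusion at 150 kg reads 125%.

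**The case against.** The bands are numeric. A 140 kg patient given 1200 mg did receive 8.57 mg/kg, so placing that infusion below 9 mg/kg is a true statement. No table is headed overdose, underdose or dosing error, and the SAP's note says what will not count as such, not that everything outside 9-11 will. Major protocol deviations are tabulated separately (SAP 3.2), and nothing derives them from these bands. All administrations are listed. This stands. A reader might infer that the plan reports correctly dosed patients as dosing errors, but the documents do not say so. What remains is that the note ties 9-11 to over- and underdose and attributes to the protocol a reference that the protocol does not use.

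The weight-change route is also weaker than it may look. A reader might infer that the dose changes only after a >10% weight change. Protocol 6.1 requires recalculation in that case but does not forbid it for smaller changes, and details are left to a pharmacy manual that is not among the documents. In Part A the last available weight will often be the one used for dosing. This stands too, so the route is stated as conditional.

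Finally, no endpoint, analysis set or event rate uses the bands, and the trial is descriptive. That limits the importance of the point but does not remove the mismatch.

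**Conclusion.** The SAP departs from the protocol rule that it cites. Its bands ignore the 1200 mg cap, so a full planned infusion above 133.3 kg is tabulated below 9 mg/kg, and an infusion well above the capped amount in a patient over 120 kg can be tabulated as 9-11 mg/kg. This part is plain arithmetic on the stated rules. The weight-loss part holds only if the dose was left unchanged and a re-measured weight shows a loss of more than 9.09% and up to 10%.

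The scope is narrow. A reader might infer that every patient of 120 kg or more is affected, or that weight gain also produces apparent underdosing. For a full planned dose, the cap matters only above 133.3 kg, and an uncapped patient's gain within 10% stays in 9-11.

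The effect is confined to a descriptive exposure table. At most 167 patients could enter (SAP 1.3), and the documents give no weight distribution. The number affected is therefore unknown, probably small and possibly zero. This is a minor correction, worth making because no other planned table summarises the amount given.

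**What to change.** Reconcile Protocol 6.1, Protocol 6.2 and SAP 3.6.2, without this review taking a position on which dose rule is right. In SAP 3.6.2:

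- Categorise the actual amount as a percentage of the protocol-planned amount: <90%, 90-110%, >110%. As the protocol now stands, the planned amount is the smaller of 10 mg/kg × dosing weight and 1200 mg.
- Use the dosing weight where it is recorded or can be derived from the weight history, and otherwise the last available weight. The fallback corrects the cap part only.
- Correct the note so that it states the tolerance as the protocol does.
- If wanted, add a descriptive statistic of actual mg/kg. None is planned at present.

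The cap part needs only volumes and weights that the SAP formula already uses, so it costs one changed derivation and one changed table stub. The weight part may cost more, because SAP 3.6.1 lists date/times and volumes as recorded for each administration but not the dosing weight.

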3.6.3 Presentation of results

A frequency table for the number of administrations per cycle and overall, and the actual dose per administration will be created.

Descriptive statistics of the overall number of administrations and treatment compliance.

All study drug administration data will be listed.

	
Statistical Analysis Plan
	

ARGX-113-1705
	
Final Analysis
	
Final 1.0 of 20SEP2022

4. EFFICACY, PHARMACODYNAMICS AND ANTI-DRUG ANTIBODIES ANALYSES

4.1 EFFICACY

4.1.1 *Available data*

Efficacy will be assessed using MG-ADL (part A and B) and QMG (part A only).

4.1.2 *Endpoints and derivation rules*

1) Actual values and change from baseline and CnB in total MG-ADL score will be analysed descriptively and categorically.

Categories to be used for actual values in MG-ADL total score: 0, 1, 2, 3, 4, 5-7, 8-9, 10-12, 13-16, 17-20 and 21-24.

Categories to be used for changes from baseline and CnB in MG-ADL total score: >0, 0, -1, -2, -3, -4, -5, -6, -7, -8, -9, -10, <-10. Number of patients, percentages and cumulative percentages will be shown.

In addition to the planned timepoints, following timepoints will be shown for each cycle:

- Maximum drop from baseline and CnB in MG-ADL
- Minimum MG-ADL score: descriptively and categorically

Missing data will not be considered.

Analysis will be done on AChR-Ab seropositive patients, AChR-Ab seronegative patients and overall.

2) Actual values and change from baseline and CnB in total QMG score will be described descriptively and categorically as for the MG-ADL score. For the categorization of the QMG total score actual values a category of >24 will be added.

4.1.3 *Statistical analysis*

Summary statistics will be provided in terms of absolute values and changes from baseline (overall) and CnB (for each cycle) for MG-ADL and QMG total scores in AChR-Ab seropositive patients, AChR-Ab seronegative patients and the overall safety population.

Absolute values and changes from baseline (overall) and CnB (for each cycle) in MG-ADL and QMG total scores will also be categorized, including the number of patients within each category, the percentage, and the cumulative percentage.

See section 8 for a list of tables and listings.

4.2 PHARMACODYNAMICS

4.2.1 *Available data*

The following pharmacodynamic parameters are collected during part A of the study and will be analysed: PD markers (total IgG and IgG subtypes [IgG1, IgG2, IgG3 and

	
Statistical Analysis Plan
	

ARGX-113-1705
	
Final Analysis
	
Final 1.0 of 20SEP2022

IgG4], and autoantibodies (anti-AChR antibodies for the AChR-Ab seropositive patients and anti-MuSK antibodies)

4.2.2 Endpoint and derivation rules

1) Change and percent change (compared to Baseline and CnB) in total IgG level and IgG subtypes [IgG1, IgG2, IgG3 and IgG4] at each visit.

Analysis will be done by AChR-Ab status and overall.

2) Change and percent change (compared to Baseline and CnB) in anti-AChR antibodies (in AChR-Ab seropositive patients) at each visit.

See section 2.2.2 for calculation of change and percent change from baseline.

Values Below the limit of quantification (BLQ) will be imputed with the lower limit of quantification. Values Above the limit of quantification (ALQ) will be excluded from the statistical analysis and will thus also not be considered for the baseline selection. Patient with a baseline value BLQ will be excluded from the statistical analysis and only be listed.

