ARGX-113-1501 was a randomized, double-blind, placebo-controlled, First-in-Human (FIH) phase 1 trial conducted in 62 healthy volunteers to assess the safety and tolerability and to evaluate the PK and PD characteristics of single and multiple ascending intravenous (IV) doses of efgartigimod. The trial showed that a single administration of efgartigimod reduced IgG levels up to 50%, while multiple dosing further lowered IgGs up to approximately 70%. IgG levels returned to baseline approximately 8 weeks following the last administration of efgartigimod. IV administration of efgartigimod at single doses up to 25 mg/kg and multiple doses of 10 mg/kg and 25 mg/kg were safe and well tolerated.

Based on an optimal PD effect combined with minimal number of observed adverse events (AEs) (compared to the 25 mg/kg dose level), the dose of 10 mg/kg once weekly for 4 weeks provided the most favorable risk-benefit profile and was therefore selected for further testing in the phase 2 trial. The outcome of the phase 2 trial indicated the efficacy and safety of 10 mg/kg in 4 weekly infusions in gMG patients

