2.2.2 Baseline and change from baseline

Two baselines are defined:

- Baseline is the last available value prior to first administration of efgartigimod in the first cycle in 1705.
- CnB: Cycle n Baseline i.e. last available value prior to first administration of efgartigimod in cycle n, with n=1, 2, 3, etc..

Note: for MG-ADL and QMG, all assessments on the day of first administration of the IMP in cycle n are considered in the baseline selection, also those post-administration.

Change can be calculated from baseline or CnB. Note: baseline coincides with C1B. Baseline will be considered for analyses that assess across all cycles and the CnB will be used for analyses restricted to a specific cycle, n.

Change for safety parameters will be calculated from baseline only.

For efficacy and PD, a (percent) change can be calculated from baseline or CnB, according to the analysis.

	Statistical Analysis Plan	
ARGX-113-1705	Final Analysis	Final 1.0 of 20SEP2022

Change from baseline at time point t = value at time point t – baseline value.

Percent change from baseline at time point t = (actual value at time point t -baseline value)*100/baseline value.

Change from CnB at time point t = value at time point t – CnB value.

Percent change from CnB at time point t = (actual value at time point t - CnB value)*100/CnB value.

2.2.3 *Relative day*

Relative days in the period (ADYP) will be calculated according to the following rule:

- Concerned date < reference date: ADYP = concerned date – reference date
- Concerned date ≥ reference date: ADYP = concerned date – reference date + 1

The reference date is the date of first administration of study drug in the specific period, except for assessments in ITP0, for which the date of informed consent in 1705 will be taken as reference date.

2.2.4 *Analysis visits*

All assessments (from first ARGX-113-1705 cycle on), including unscheduled assessments, will be allocated to analysis windows. Tables and listings will present the analysis windows as defined below, not the CRF visits. Allocation of assessments will be done using their relative day in the period (see section 2.2.3).

Table 4: Analysis visits

Phase/Period	Analysis window	Target ADYP	Lower limit ADYP	Upper limit ADYP
Treatment/ cycle n (=Treatment Period n + ITP_n)				
	CnB	1	-INF	1*
	Week 1	8	1*	11
	Week 2	15	12	18
	Week 3	22	19	35
	Week 7	50	36	63
	Week 7 + (4*x)	50 + (x*28)	50 + (x*28) - 14	50 + (x*28) + 13

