* An assessment on day 1 will be attributed to CnB in case it is before the infusion, to week 1 otherwise, except for MG-ADL and QMG (see section 2.2.2)

Baseline is defined in section 2.2.2.

For those patients who will start a new cycle, the last assessment in a cycle, prior to the infusion of the new cycle, will be allocated to the appropriate visit within the previous cycle and will also be allocated as the CB visit of the new cycle.

Per parameter and analysis window, the value closest to the target ADYP will be used in analysis tables and figures, other values will only be listed. If more than one value is located at the same distance from the target, then the latest in time will be selected.

	
Statistical Analysis Plan
	

ARGX-113-1705
	
Final Analysis
	
Final 1.0 of 20SEP2022

The value latest in time will be identified using, in order of preference, the assessment time, the visit label or the group identifier. Missing values are removed before the selection is made.

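### A PD cycle baseline can fall back to a drug-suppressed sample from the previous cycle when the visit 1 value is above the quantification limit or missing

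*SAP*

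**What the plan says.** - SAP 4.2.2 sets PD values below the limit (BLQ) to the lower limit of quantification. ALQ values "will be excluded from the statistical analysis and will thus also not be considered for the baseline selection". For a low baseline the rule differs: "Patient with a baseline value BLQ will be excluded from the statistical analysis and only be listed".
- SAP 2.2.2 defines CnB as "Cycle n Baseline i.e. last available value prior to first administration of efgartigimod in cycle n". In Table 4 (SAP 2.2.4) the CnB window has a lower limit of minus infinity and an upper limit of day 1.
- SAP 2.2.4 states that, for patients starting a new cycle, the last assessment before the new infusion stays in its own cycle and "will also be allocated as the CB visit of the new cycle". On selection it says: "Per parameter and analysis window, the value closest to the target ADYP will be used in analysis tables and figures". Missing values are removed before selecting.
- Protocol 4.1 and Section 5 set the baseline of each treatment period at visit 1 of that period. Protocol 3.3 defines the PD endpoints as percentage decreases from TP1B and from the corresponding TPnB.
- Protocol Table 1, PD footnote: "Samples for pharmacodynamic (PD) biomarkers will be collected predose on dosing days". PD is scheduled at all four treatment visits and at each intertreatment visit in Part A. It is not scheduled in Part B.

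**The concern.** Each rule is ordinary alone. Together they let the plan discard the sample meant to be the cycle baseline and substitute an older one without a flag. The older sample may have been taken while IgG was still suppressed by the previous cycle.

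In the ALQ case the error has one direction. The discarded value is above the limit and its replacement is not, so CnB is too low and the percentage decrease is understated. Dropping ALQ values also removes the largest observations from the absolute-value summaries, which biases those downward. At stake are the change-from-CnB tables for IgG, IgG subtypes and anti-AChR antibodies.

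**Working it through.** The plan gives no figure to reproduce: no upper limit of quantification (ULOQ), no ALQ frequency and no expected size of change. The check traces the rule and then illustrates it.

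**Inputs from the documents**
- Depth: "multiple dosing further lowered IgGs up to approximately 70" percent (Protocol 1.2, phase 1).
- Recovery: IgG back to baseline about 8 weeks (56 days) after the last dose (Protocol 1.2).
- Part A intertreatment visits: every 30 days after the previous visit (Protocol Table 1).
- Re-treatment in Part A: allowed after visit 4 once the MG-ADL criteria are met; the listed criteria set no minimum interval (Protocol 4.1).
- Percent change = (value - CnB) × 100 / CnB (SAP 2.2.2).

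**Assumptions**
- Pre-treatment level = 100. Nadir N = 30 or 35. The visit 4 sample, taken before the fourth infusion, is treated as the nadir.
- Linear recovery: level at day d = 100 - (100 - N)(1 - d/56), and 100 from day 56.
- Exponential recovery, 5% of the reduction left at day 56: level = 100 - (100 - N)·exp(-d·ln 20/56).
- The new cycle reaches the same nadir N.

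**Which sample becomes CnB if visit 1 is ALQ or missing?** The one 30 days earlier. For re-treatment 30 days after visit 4 this is the visit 4 sample. At 60 days it is the day-30 sample, and at 90 days the day-60 sample.

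**Example (N = 30, linear, re-treatment at day 30).** Visit 1 level = 100 - 70 × (1 - 30/56) = 67.5. Correct change = (30 - 67.5)/67.5 = -55.6%. With the fallback: (30 - 30)/30 = 0%.

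| Re-treatment | N, recovery | Visit 1 level | Fallback level | Correct change | Change with fallback | Error (points) |
|---|---|---|---|---|---|---|
| 30 days | 30, linear | 67.5 | 30 | -55.6% | 0% | 55.6 |
| 30 days | 30, exponential | 85.9 | 30 | -65.1% | 0% | 65.1 |
| 30 days | 35, linear | 69.8 | 35 | -49.9% | 0% | 49.9 |
| 30 days | 35, exponential | 86.9 | 35 | -59.7% | 0% | 59.7 |
| 60 days | 30, linear | 100 | 67.5 | -70.0% | -55.6% | 14.4 |
| 60 days | 30, exponential | 97.2 | 85.9 | -69.1% | -65.1% | 4.0 |
| 60 days | 35, linear | 100 | 69.8 | -65.0% | -49.9% | 15.1 |
| 60 days | 35, exponential | 97.4 | 86.9 | -64.1% | -59.7% | 4.3 |
| 90 days | any of the four | 99 to 100 | 97 to 100 | -65% to -70% | -64% to -70% | under 1 |

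**Effect on a cycle mean.** Shift = share of patient-cycles affected × error per patient. If every affected cycle is re-treated at 30 days, 1% affected moves the mean by 0.01 × 50 to 65 = 0.50 to 0.65 points, and 5% by 2.5 to 3.3 points. At 60 days, 1% affected moves it by 0.04 to 0.15 points.

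**How high must the patient be for the ALQ route at day 30?** The visit 1 level is then 67.5% to 86.9% of pre-treatment. It exceeds the ULOQ only if the pre-treatment level is above about 1/0.869 = 1.15 to 1/0.675 = 1.48 times the ULOQ. A missing sample needs no such condition.

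**The case against.** The strongest reply is that the fallback will seldom occur. A predose PD sample is scheduled at every visit 1, and Appendix 8 requires the patient to be on site to start a treatment period. The ALQ route also works against itself: it does most harm at short intervals, when IgG is still partly suppressed and least likely to exceed the limit. Last available pre-dose value is a common convention, PD is tertiary and descriptive, and SAP 4.2.3 lists all data. All of this stands and limits the size. It does not remove the rule, because the tables would carry a substituted baseline without a flag or count.

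Three stronger readings might be inferred and are not supported:
- *The error is the full 65 to 70 points.* That compares the fallback with a fully recovered visit 1 value at day 30. Protocol 1.2 puts recovery at about 8 weeks, so the fair comparator is a partly recovered value.
- *The patients with the highest titres drop out.* SAP 4.2.2 excludes ALQ values, not patients; a patient's other values stay in.
- *Setting ALQ baselines to the ULOQ merely mirrors the BLQ rule.* At baseline, the BLQ rule excludes the patient. ULOQ substitution is a separate choice with its own known bias.

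**Conclusion.** The point holds as a defect in a stated rule. Followed exactly, the SAP can replace an ALQ or missing visit 1 PD value with a sample from the previous cycle, whereas the protocol fixes the period baseline at visit 1. Under the assumed recovery shapes and a nadir of 30% to 35%, re-treatment at 30 days gives about 0% instead of roughly -50% to -60%, with -65% for the deepest nadir and faster early recovery. The error shrinks to about 4 to 15 points at 60 days and is negligible from 90 days.

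The shift in a mean depends on how often this occurs. The documents do not say, so the 0.5 to 0.65 points per 1% affected is a ceiling that assumes 30-day re-treatment throughout. The figures concern IgG; the documents give no depth or recovery time for anti-AChR antibodies.

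The scope is narrow: descriptive tertiary PD summaries from Part A. The safety endpoints are untouched. From cycle 2 onward, change from overall Baseline keeps its own baseline. In cycle 1 the two coincide, and the SAP does not say whether a value from trial ARGX-113-1704 may serve if the first value here is ALQ.

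**What to change.** In SAP 4.2.2, for PD only:
1. Take CnB from the predose visit 1 sample of cycle n, or from a short stated window before the first infusion. Otherwise CnB is missing for that cycle.
2. Keep ALQ values in the absolute-value summaries at the ULOQ, flagged.
3. For an ALQ baseline, choose one rule in advance. Either use the ULOQ with a flag, which understates the decrease in a known direction, or exclude that patient-cycle from the change tables, parallel to the existing rule for a BLQ baseline.
4. Report the number of ALQ values per cycle.

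This takes a few sentences and one count, with no new data. The price is that a few cycle baselines become missing.
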